2.2. Study Endpoints

2.2.1. Primary Endpoint:

- Objective radiographic response (ORR), as measured by modified Response Assessment in Neuro-Oncology (RANO) criteria

2.2.2. Secondary Endpoints:

- Safety and tolerability will be assessed by monitoring frequency, duration, and severity of adverse events (AEs) through physical examinations, by evaluating changes in vital signs, and through clinical laboratory evaluations.
- OS, defined as the time from date of enrollment until death from any cause
- PFS, defined as the time from date of enrollment until the earliest date of disease progression (as determined by modified RANO criteria) or death due to any cause

2.2.3 Exploratory Endpoints:

- Comparison of the following immunocorrelative assays in subjects treated with INCMGA00012 + INCAGN01876, with or without SRS:
 - Multiplex immunohistochemistry on tumor tissue for CD4/8 T cell infiltration, Foxp3+ Treg infiltration, and PD-1/PD-L1 expression
 - Tumor cell and immune cell GITR expression by a validated immunohistochemistry stain
 - Flow cytometry/mass cytometry in tumor tissue and peripheral blood for T cell and monocyte phenotyping
 - RNA-Seq on tumor tissue for PD-1/PD-L1 and GITR expression, T cell- and interferon- γ -related gene expression, and cell-cycle-related gene expression
 - T cell receptor sequencing in tumor tissue and peripheral blood for assessment of TCR clonal diversity
- Association between the above tumor tissue and peripheral blood-based markers of immune activation, tumor genetic mutations, and clinical outcomes of OS, PFS, and ORR
- PK parameters for INCAGN01876 in patients with glioblastoma
- Detection of anti-drug antibodies (ADA) against INCAGN01876

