In both surgical sub-arms, within 7 days of enrollment the subject will receive a single dose of the investigational systemic agent(s) according to the sub-arm to which he/she is assigned. In sub-arm # 1 (INCMAG00012 + INCAGN01876 + SRS), within 3 to 7 days following the neoadjuvant doses of the systemic study drugs, the subject will receive SRS, administered over the course of 3 consecutive business days (8 Gy x 3 fractions, one fraction per day, total dose 24 Gy). Subjects may receive 3 fractions every other day (non-consecutively) for logistical reasons relating to COVID-19. Within 7-14 days following administration of the study drug(s) (surgical sub-arms # 2) or within 7-14 days following SRS (surgical sub-arm # 1), the subject will undergo maximal safe surgical resection of the tumor. Following surgery, the subject will then resume systemic therapy with BOTH investigational agents INCMGA00012 and INCAGN01876 (regardless of which of the two sub-arms the subject was assigned to). The systemic agents should be started as soon as the investigator feels the subject has recovered adequately from surgery, but must be restarted within 5 weeks (35 days) from the date of surgery. Subjects will continue on combined systemic treatment (INCMGA00012 500 mg IV every 4 weeks and INCAGN01876 300mg IV every 2 weeks) until disease progression, unacceptable AEs, or for 2 years, whichever occurs first.

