As long as the subject has not withdrawn his/her consent, the non-treated (replaced) subject is followed for safety follow-up per [Table 10](#) (see [Section 6](#)) and all safety-related data collected for the subject is included in analysis of the study's secondary safety/tolerability endpoints. However, the subject is not included in the primary endpoint efficacy analysis or in analysis of secondary efficacy endpoints (see [Section 8, Statistical Plan](#)). In addition, if the replaced subject was enrolled during the safety run-in phase, that subject will not be counted for purposes of determining whether the pre-specified safety criteria (see [Section 3.1; General Design](#)) have been met during the safety run-in phase to allow for successful completion of the safety run-in phase.

Subject replacement occurs up to and no more than 7 times for Cohort A [i.e., up to 23 subjects can be enrolled to obtain 16 subjects who receive both of the study drugs at the same dose and schedule AND SRS and are therefore evaluable for the primary endpoint].

Cohort B: Any subject who is enrolled onto Cohort B of the study but meets one of the following criteria is replaced by enrollment of a new subject onto Cohort B:

- The subject is enrolled, but does not receive either of the systemic agents (INCMGA00012, INCAGN01876)
- The subject is enrolled, but does not receive SRS (surgical subarm #1 only)
- The subject is enrolled, but does not undergo surgery

As long as the subject has not withdrawn his/her consent, the non-treated (replaced) subject is followed for safety follow-up per [Table 10](#) (see [Section 6](#)) and all safety-related data collected for the subject is included in analysis of secondary study endpoints.

Subject replacement occurs up to and no more than 10 times for Cohort B [i.e., up to 26 subjects can be enrolled to obtain 16 subjects who receive neoadjuvant therapy AND undergo surgery, with 8 patients assigned to each of the 2 sub-arms]. Subjects who need to be replaced in Cohort B, will be replaced by a subject enrolled onto the same sub-arm that the replaced subject was previously on.

Replaced subjects will be followed for safety only. These subjects will not be included in efficacy endpoint analyses, and they will not have tumor tissue available for correlative endpoint analyses.

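### Cohort B survival is timed from enrollment but reported only for subjects who reach surgery, which biases OS, and to a lesser extent PFS, upward

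*Combined protocol and SAP*

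**What the plan says.** Section 2.2.2 sets both time origins at enrollment: "OS, defined as the time from date of enrollment until death from any cause" and "PFS, defined as the time from date of enrollment until the earliest date of disease progression".

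Section 3.2 lists three triggers for replacing a Cohort B subject. The third is "The subject is enrolled, but does not undergo surgery". It carries no condition on the reason, or on whether drug or SRS has already been given. The consequences are "Replaced subjects will be followed for safety only" and "These subjects will not be included in efficacy endpoint analyses". The limit is stated as "Subject replacement occurs up to and no more than 10 times for Cohort B", with up to 26 enrolled to obtain 16 who have neoadjuvant therapy and surgery.

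Section 3.1.2 places surgery after treatment. The first dose falls within 7 days of enrollment. Surgery follows 7-14 days after drug in sub-arm 2, or 7-14 days after SRS in sub-arm 1.

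Section 8.2.2 plans Kaplan-Meier estimates of PFS and OS and exploratory log-rank tests of Cohort A against Cohort B. It names no analysis set for PFS or OS, no landmark or delayed entry, and no sensitivity analysis that brings replaced subjects back. The synopsis limits Cohort B efficacy to descriptive statistics.

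**The concern.** Membership of the analysed set is decided by something that happens after time zero. An operated subject contributes the interval from enrollment to surgery as survival time, while a subject who dies in that interval contributes nothing. This is immortal-time bias, and it acts on a descriptive curve just as it acts on a test.

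A second effect points the same way. A subject who has been dosed and then becomes too ill for surgery is removed together with all later follow-up, so the remaining set is enriched for better prognosis. Some of those removed have already met the protocol's own event definition: Section 7.7.2 counts clear clinical deterioration, and failure to return because of death or a deteriorating condition, as progressive disease. Such decline is foreseeable, since Section 5.8.3 expects SRS to cause cerebral edema and Section 12.1 names edema as the likeliest cause of a drug-related serious event.

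At stake are the Cohort B PFS and OS estimates and their comparison with Cohort A. If follow-up really is limited to safety, the data needed to correct the estimates may never be collected.

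**Working it through.** **Replacement ceiling.** 16 + 10 = 26, as stated in Section 3.2. The ceiling as a share of enrollment is 10/26 = 38.5%. It counts every replacement, including subjects never dosed.

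**Guaranteed time from enrollment** (windows from Section 3.1.2; days to dose + dose to SRS start + span of SRS + wait to surgery):

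- Sub-arm 1: shortest 0 + 3 + 2 + 7 = 12 days; longest 7 + 7 + 4 + 14 = 32 days, with fractions every other day.
- Sub-arm 2: shortest 0 + 7 = 7 days; longest 7 + 14 = 21 days.
- Cohort A, to the first SRS fraction: shortest 0 + 3 = 3 days; longest 7 + 7 = 14 days. Cohort A is the right comparator because Section 3.2 also replaces its subjects who do not receive SRS and leaves them out of secondary efficacy analyses.

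**Effect of guaranteed time alone on median OS.** Assume exponential survival with median M = 11 months. Section 1.2 reports a median of about 11 months after re-irradiation in a retrospective series, and under 12 months for recurrent disease generally. Requiring survival to time t0 while counting from enrollment moves the median from M to M + t0.

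- t0 = 7 days: 7/30.4375 = 0.23 month, or 0.23/11 = 2%.
- t0 = 32 days: 32/30.4375 = 1.05 months, or 1.05/11 = 10%.

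The expected proportion dying before surgery is 1 − 2^(−t0/M), which is 1.4% at 7 days and 6.4% at 32 days. For 26 enrolled that is 0.4 to 1.7 deaths.

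**Effect of selective removal (illustration only).** The documents give neither the number who will miss surgery nor their prognosis. Take 16 operated subjects with median OS of 11 months from surgery at day 21 (t0 = 0.69 month), and k non-operated subjects whose hazard from enrollment is h times as high. For all subjects together, at t beyond t0:

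S(t) = [16/(16+k)] × 2^(−(t−t0)/11) + [k/(16+k)] × 2^(−h·t/11)

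| Set | h | Median OS (months) | 6-month OS |
|---|---|---|---|
| Operated only | – | 11.7 | 0.72 |
| k = 4 added | 1 | 11.6 | 0.71 |
| k = 4 added | 2 | 10.0 | 0.67 |
| k = 4 added | 3 | 9.3 | 0.64 |
| k = 10 added | 1 | 11.4 | 0.70 |
| k = 10 added | 2 | 8.7 | 0.62 |
| k = 10 added | 3 | 7.4 | 0.56 |

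With equal hazards the difference is at most about 0.3 month. It becomes material only if non-operated subjects do clearly worse and there are several of them.

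**PFS.** The guarantee is weaker here. The trigger is absence of surgery, not progression, and Table 9 schedules no restaging MRI between screening and surgery. A subject who progresses but is still operated on stays in. The bias reaches PFS only where death or deterioration stops the operation, so no separate PFS figure is given.

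**The case against.** The strongest reply is that Cohort B is an exploratory tissue cohort, that its efficacy is descriptive, that the operated-only rule is stated openly in advance, and that with 8 subjects per sub-arm a shift of up to a month would probably be lost in sampling error. All of this limits the importance of the point. None of it removes the bias: a descriptive median with a known upward error is still misleading, and Section 8.2.2 does plan a log-rank test that uses it.

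Several stronger readings are tempting and should be resisted.

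- A reader might take 10/26 as the share of treated subjects who vanish. It is a cap on all replacements, whatever the cause, and includes undosed subjects.
- A reader might construct an example in which 12 of 20 alive at 6 months (60%) becomes 12 of 16 (75%). That requires four treated subjects to be lost and all four dead by 6 months. This is close to a worst case given entry criteria of Karnofsky 60 or above and life expectancy over 3 months.
- A reader might say that a stated secondary objective is compromised for the whole cohort. Section 2.1.2 words that objective for patients given both drugs and SRS, so within Cohort B it covers only sub-arm 1.
- A reader might say that a harmful neoadjuvant phase would be concealed. Section 3.2 keeps the safety data of replaced subjects and Section 8.2.2 puts everyone who consents into the safety analyses. Only the efficacy summary would miss the harm.

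**Conclusion.** The point stands at moderate weight. As written, the plan conditions Cohort B PFS and OS on an event about 7 to 32 days after time zero. OS is biased upward, as is PFS where death or deterioration prevents surgery. The A-versus-B log-rank inherits an imbalance in Cohort B's favour on this point, because the guaranteed windows differ (7-32 days against 3-14).

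The part that follows from the protocol windows is about 0.2 to 1 month on median OS, assuming exponential survival and an 11-month median. The part due to selective removal ranges from negligible to several months, depending on a non-operation rate and a prognosis that the documents do not give. It should be treated as unknown. The primary response test uses Cohort A only and is not affected.

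**What to change.** 1. Keep the replacement rule for the tissue endpoints, so that 8 operated subjects per sub-arm are still obtained.
2. In Section 8.2.2, define the Cohort B PFS and OS set as all enrolled subjects timed from enrollment, or all dosed subjects timed from first dose. A set defined by dosing but timed from enrollment would retain up to 7 days of guaranteed time.
3. Start any operated-only summary at the date of surgery and label it as such.
4. Reconcile the follow-up text. Section 3.2 limits replaced subjects to safety follow-up. Section 3.3 sends subjects who stop study drug without withdrawing consent into the follow-up period, and Table 10 already has a disease-status and survival column. State that replaced subjects who have not withdrawn consent are followed under that column.
5. Apply the same principle to Cohort A in the exploratory log-rank, so that both cohorts are analysed from the same kind of time origin.

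The cost is disease-status and survival follow-up of at most 10 more Cohort B subjects, plus any replaced Cohort A subjects brought in under item 5, using contacts already described in Section 3.1.3, and possibly less favourable estimates. Treatment and the tissue sample size do not change.

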3.3. Duration of Individual Subject Study Participation

After signing the ICF, screening procedures commence. Each enrolled subject begins study treatment. Treatment continues until the subject meets any one or more of the criteria for study drug discontinuation (see [Section 5.7; Study Drug Discontinuation Criteria](#)). When a subject discontinues study drug but has not withdrawn consent, the subject enters the follow-up period. Subjects are taken off study if any of the following criteria apply:

- Lost to follow-up
- Withdrawal of consent
- Death
- Sponsor decides to terminate the study

3.4. Overall Study Duration

The study begins at the time that it becomes actively open to patient enrollment (i.e., the site is activated for the trial and screening for subjects has commenced). The study ends when all subjects have discontinued the study and the last follow-up visit has been performed.

In addition, the sponsor may terminate the study if required by regulatory decision, or upon review of emerging data. If the study is terminated prematurely, the sponsor will notify the principal investigator and the FDA of the decision and reason for termination of the study.

3.5 Total Number of Subjects and Sites

This is a single center study and subjects are only recruited from the University of Pennsylvania. Recruitment for Cohort A ends when (1) the safety run-in phase has been successfully completed AND (2) 16 subjects in Cohort A have received at least one dose of each study drug at the same dose/schedule as determined by the safety run-in phase. Greater than 16 total subjects may be enrolled on Cohort A if the stopping rule for toxicity is met during the safety run-in phase (see [Section 3.1 General Design](#)). The maximum possible sample size for Cohort A is 22 subjects who are evaluable for the study's primary efficacy endpoint, which would occur if enrollment of 12 subjects (which is the maximum allowed for the safety run-in phase) is necessary to successfully complete the safety run-in phase and an additional 10 subjects are enrolled at the same finalized dose/schedule of study drugs that was given to the last 6 subjects enrolled on the safety run-on phase.

Recruitment for Cohort B ends with 16 subjects have received study drug(s) AND surgery.

4. INCLUSION AND EXCLUSION CRITERIA

4.1 Inclusion Criteria

Subjects must meet all of the following criteria:

1. Prior histopathologically proven diagnosis of World Health Organization (WHO) grade IV glioblastoma, OR histopathologically proven diagnosis of gliosarcoma, OR molecular diagnosis of glioblastoma per c-IMPACT-NOW criteria (“diffuse astrocytic glioma, IDH-wildtype, with molecular features of glioblastoma, WHO grade IV”; this requires presence of either amplification of *EGFR*, whole chromosome 7 gain AND whole chromosome 10 loss, or *TERT*

promoter mutation). Participants are eligible if the prior diagnosis was low-grade glioma and a subsequent histological diagnosis of glioblastoma was made (e.g. secondary GBM).

2. Participants must have glial tumor that is recurrent following prior first-line radiation therapy (prior dose must have been 40-75 Gy and may have been either photon or proton radiation), and must have unequivocal evidence of tumor progression by MRI scan

3. Cohort A and Sub-Arm 1 of Cohort B only: Patient must have at least one measurable (≥ 1 cm x 1 cm) contrast-enhancing tumor focus for which stereotactic radiosurgery (SRS) is clinically indicated, as determined by the Investigator, and must be able to achieve radiation target coverage without exceeding dose constraints. The contrast-enhancing target must not be larger than 4 cm in maximal diameter. Multifocal disease is allowed as long as this criterion is met

- Sub-Arms 2 of Cohort B can have any size tumor, and the tumor does not need to be amenable to SRS

4. Cohort B (surgical) patients only: patients must be undergoing surgery that is clinically indicated as determined by their care providers

5. Tumor O-6-methylguanine-deoxyribonucleic acid (DNA) methyltransferase (MGMT) methylation status must be available from any prior GBM tumor specimen; results of routinely used methods for MGMT methylation testing (e.g. mutagenically separated polymerase chain reaction [MSPCR] or quantitative polymerase chain reaction [PCR]) are acceptable)

6. Patients may have had treatment for an unlimited number of prior relapses but must not have had prior bevacizumab or other vascular endothelial growth factor (VEGF/VEGFR) inhibitors (exception: prior bevacizumab is allowed if it was administered for the treatment of radiation necrosis rather than progressive tumor and was stopped at least 4 weeks prior to MRI showing demonstrating tumor progression). Prior gliadel wafers are only allowed if placed during the first surgery for GBM at initial diagnosis.

7. Patients must have recovered from severe toxicity of prior therapy; the following intervals from previous treatments are required to be eligible:

- 12 weeks from completion of radiation
- 6 weeks from a nitrosourea cytotoxic chemotherapy
- 3 weeks from a non-nitrosourea cytotoxic chemotherapy
- 4 weeks from any investigational (not Food and Drug Administration [FDA]-approved for glioblastoma) agents, or within a time interval less than at least 5 half-lives of the investigational agent whichever is shorter
- 3 weeks from any major surgery, including brain surgery for recurrent tumor resection

8. If patient is on systemic corticosteroids to treat brain edema and/or brain edema-related symptoms, the dose must be 2mg of dexamethasone (or equivalent) daily or less for a minimum of 5 days prior to first dose of study drug.

9. Patients must be able to swallow oral medications

10. Age 18 or older

11. Karnofsky performance status ≥ 60
12. Life expectancy >3 months
13. Absolute lymphocyte count $\geq 500/uL$
14. Adequate hepatic function within 7 days prior to start of study treatment, defined as follows
 - Total bilirubin (except patients with Gilbert's Syndrome, who are eligible for the study but exempt from the total bilirubin eligibility criterion) ≤ 2.0 mg/dl
 - ALT and AST $\leq 2.5x$ upper limit of normal (ULN)
15. Adequate renal function within 7 days prior to start of study treatment, defined as follows:
 - Serum creatinine ≤ 1.5 x institutional ULN OR calculated creatinine clearance (glomerular filtration rate can also be used in place of creatinine or CrCl) ≥ 50 mL/min for subjects with creatinine levels $>1.5x$ institutional ULN
16. Reproductive Status
 - a) Women of childbearing potential (WOCBP) must have a negative serum or urine pregnancy test (minimum sensitivity 25 IU/L or equivalent units of HCG) within 7 days prior to the start of study drug.
 - b) Women must agree to not breastfeed during the study or for 180 days after the last dose of study treatment
 - c) WOCBP must agree to use an adequate method to avoid pregnancy (as defined below) from the time of study screening through 180 days from last dose of study drug
 - d) Males who are sexually active with WOCBP must agree to follow instructions for method(s) of contraception (as defined below) starting with the first dose of study drug through 180 days after the last dose of study
 - e) Azoospermic males and WOCBP who are continuously not heterosexually active are exempt from contraceptive requirements. However, these WOCBP must still undergo pregnancy testing as described in this section.

At a minimum, participants of childbearing potential who are sexually active and their partners must agree to the use of a highly effective form of contraception (as defined below) throughout their participation beginning with the time of consent, during the study treatment, and for 180 days after last dose of study treatment(s).

HIGHLY EFFECTIVE METHODS OF CONTRACEPTION:

- Hormonal methods of contraception including combined oral contraceptive pills, vaginal ring, injectables, implants and intrauterine devices (IUDs) by WOCBP subject or male subject's WOCBP partner. Female partners of male subjects participating in the study may use hormone-based contraceptives as one of the acceptable methods of contraception since they will not be receiving study drug
- Nonhormonal IUDs
- Bilateral Tubal ligation
- Vasectomy
- Sexual Abstinence

- It is not necessary to use any other method of contraception when complete abstinence is elected.
- WOCBP participants who choose complete abstinence must continue to have pregnancy tests.
- Acceptable alternate methods of highly effective contraception must be discussed in the event that the WOCBP participants chooses to forego complete abstinence.

17. Participant must, in the opinion of the Investigator, be able to comply with study procedures

18. Patients must be able to understand the study procedures and agree to participate in the study by providing written informed consent (or have legally authorized representative sign on patient's behalf if patient physically unable to sign consent due to neurologic deficit)

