6 STUDY PROCEDURES

Screening assessments are to be conducted within 14 days prior to initiating protocol therapy unless otherwise specified. Screening assessments occurring prior to initiating study treatment do not need to be repeated on Cycle 1 Day 1 unless otherwise specified. Screening laboratory assessments must be done within 7 days prior to initiating protocol therapy.

For women of childbearing potential, as defined in the eligibility criteria, a pregnancy test must be completed within 7 days prior to initiating protocol therapy. If a urine pregnancy test is positive or cannot be confirmed as negative, a serum pregnancy test will be required.

The schedule of study procedures for the screening and intervention phases of the study for Cohort A is displayed in **Table 8** and for Cohort B in **Table 9**. The schedule of procedures for the follow-up phase of the study for both cohorts is displayed in **Table 10**.

Table 8: COHORT A (N=16): Schedule of Study Procedures, SCREENING AND INTERVENTION

Study Week	Screen	W1	W1	W2	W3	W5	W7	Q 4 weeks		Q 8 weeks	EOT§
								Cycle X	Cycle X	Cycle X (pre-odd cycles only)	
Cycle # (28-day cycles)		Cycle 1	Cycle 1	Cycle 1	Cycle 1	Cycle 2	Cycle 2	Cycle X	Cycle X	Cycle X (pre-odd cycles only)	
Day (and window)	-14 to 1	1	5 ± 2	8	15 ± 2	1 ± 2	15 ± 2	1 ± 2	15 ± 2	1 ± 2	
Informed Consent	X										
Review Inclusion/Exclusion Criteria (Section 4)	X										
Karnofsky Performance Status (Section 7)	X	X			X	X	X	X	X		X
Demographics/Medical History (Section 7)	X										
Physical Assessment (targeted after screening visit) (Section 7)	X	X			X	X	X	X	X	X	X
Vital Signs: BP, HR, RR (Section 7)	X	X			X	X	X	X	X		X
ECG (Section 7)											
Weight (Section 7)	X	X				X		X			X
Height (Section 7)	X										
Pregnancy Test (Section 7; within 7d of first dose of study drug)	X							X			X
Concomitant Medications (Section 7)	X	X			X	X	X	X	X		X

Study Week	Screen	W1	W1	W2	W3	W5	W7	Q 4 weeks		Q 8 weeks	EOT§
Cycle # (28-day cycles)		Cycle 1	Cycle 1	Cycle 1	Cycle 1	Cycle 2	Cycle 2	Cycle X	Cycle X	Cycle X (pre-odd cycles only)	
Day (and window)	-14 to 1	1	5 ± 2	8	15 ± 2	1 ± 2	15 ± 2	1 ± 2	15 ± 2	1 ± 2	
Clinical Laboratory Evaluation – non-endocrine (CBC, CMP, Mag, Phos, LDH) (Section 7; within 7d of first dose of study drug; Labs can be collected up to -3 days prior to treatment).	X	X			X	X	X	X	X		X
HBV/HCV screening (Section 7)	X										

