7.7.4. MRI Procedures

MRI of the brain is performed once every 8 weeks on study as per standard of care for the management of recurrent GBM. The MRIs performed for this study do not include experimental sequences or coils or any experimental contrast. These MRIs do require the use of an FDA-approved gadolinium-based contrast agent. The gadolinium will be used in accordance with the FDA label for gadolinium-based contrast.

IV Line Placement – This is required to administer the contrast agent. Multiple needlesticks may be necessary if a vein cannot be properly accessed and this will be carried out with the subjects' permission.

IV Contrast Risks- As mention above, part of the MRI study will require the injection of a gadolinium contrast agent into the blood stream. There is a rare possibility that the subject could have an adverse reaction to the contrast agent such as rash, hives, itching, mild headache and nausea. The subject may also experience some minor discomfort and low risk of bleeding, infection and bruising associated with Intravenous catheter placement. Recently, FDA has also required a new class warning for all gadolinium-based contrast agents (GBCAs) for MRI concerning gadolinium remaining in patients' bodies, including the brain, for months to years after receiving these drugs. The long-term risks of this retention are not well elucidated; Gadolinium retention has not been directly linked to adverse health effects in patients with normal kidney function, and the FDA has concluded that the benefit of all approved GBCAs continues to outweigh any potential risks. Also, there is a possible risk of nephrogenic systemic fibrosis (NSF, also

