referred to as nephrogenic fibrosing dermopathy or NFD) occurring following administration of a GBCA in subjects with known moderate to severe renal disease (with a glomerular filtration rate or GFR < 30 mL/min/1.73m²). However, such patients are not eligible for this trial (see [Section 4; Eligibility Criteria](#)). In addition, serial creatinine values will be checked for each subject once monthly throughout the course of the trial. If at any point a subject's GFR falls below 30 mL/min/1.73m² or a rise in creatinine above baseline suggests an acute kidney injury, that subject must undergo a repeat serum creatinine test within 24 hours prior to the next planned MRI scan with contrast. This MRI with contrast should not be performed until the GFR is above 30 mL/min/1.73m² and is stable improving on two additional tests each separated by 48 hours.

Pregnancy Clause - Although there are no known risks related to MRI on pregnant women or a fetus, there is a possibility of yet undiscovered pregnancy related risks. Since there is potential danger to the fetus from participating in this protocol for a pregnant woman, we will exclude pregnant women. A negative urine or serum pregnancy test will be required before a woman of child-bearing potential can participate in this study. If the subject is post-menopausal for at least one year or has undergone a hysterectomy, the subject will not be required to undergo a pregnancy test prior to enrolling in this study and undergoing MRI scans. Gadolinium-based IV contrast agents are not approved in pregnant women (pregnant women will be excluded from this trial).

Metallic Foreign Fragments/Flying Object Clause -The known risks associated with this study are minimal. Implanted medical devices and metallic foreign fragments inside the body may pose a risk if you were to enter the MRI magnet room. Therefore, questions regarding medical and work history will be asked prior to the exam. The greatest risk is a magnetic object flying through the air toward the magnet and hitting the subject. To reduce this risk, we require that all people involved with the study remove all magnetic metal from their clothing and all magnetic metal objects from their pockets. No magnetic metal objects are allowed to be brought into the magnet room at any time except by approved personnel. In addition, once subject is in the magnet, the door to the room will be closed so that no one inadvertently walks into the room.

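### Section 7.7.4 says patients with GFR below 30 mL/min/1.73m² are ineligible, but inclusion criterion 15 does not ensure it

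*Combined protocol and SAP*

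**What the plan says.** Section 7.7.4 (MRI Procedures) describes the fibrosis risk of gadolinium contrast "in subjects with known moderate to severe renal disease (with a glomerular filtration rate or GFR < 30" mL/min/1.73m², and closes it with the statement "However, such patients are not eligible for this trial", referring to Section 4.

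Section 4.1, inclusion 15, defines adequate renal function as "Serum creatinine ≤ 1.5 x institutional ULN OR calculated creatinine clearance (glomerular filtration rate can also be used in place of creatinine or CrCl") of at least 50 mL/min. The last words of the item tie that floor to subjects whose creatinine is above 1.5×ULN.

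Section 7.7.4 has three further safeguards:

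- a label commitment: "The gadolinium will be used in accordance with the FDA label for gadolinium-based contrast";
- monitoring: "serial creatinine values will be checked for each subject once monthly throughout the course of the trial";
- a contrast hold, which applies if GFR falls below 30 "or a rise in creatinine above baseline suggests an acute kidney injury". It requires a repeat creatinine within 24 hours before the next contrast scan, and adds: "This MRI with contrast should not be performed until the GFR is above 30" mL/min/1.73m², with two further tests.

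On timing, Section 6 says "Screening assessments are to be conducted within 14 days prior to initiating protocol therapy unless otherwise specified". It sets a shorter window, 7 days, for screening laboratory tests. The screening MRI falls under the general 14-day rule.

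**The concern.** Section 7.7.4 treats eligibility as the barrier that keeps patients with GFR below 30 away from repeated contrast scans. If Section 4 does not create that barrier, a safety assurance that an IRB or investigator may rely on is not true as written. The later safeguards may also have been drafted on the premise that such patients had already been removed.

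What is at stake is a safety and eligibility inconsistency. It does not touch sample size or error rates, and has no material effect on the primary analysis. Section 8.1 makes response binary, so a subject without a complete or partial response counts as a non-response.

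**Working it through.** **Step 1. Does any criterion in Section 4 exclude GFR below 30?**

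- Inclusion 15, first route: creatinine ≤ 1.5×ULN. It is joined by OR, so it suffices alone.
- Inclusion 15, second route: clearance or GFR ≥ 50 mL/min, for subjects with creatinine above 1.5×ULN. It does not constrain anyone who entered by the first route.
- GFR may be used in place of creatinine or clearance; it is not required.
- Inclusion 17 (ability to comply) and exclusion 13 (undue risk from study treatment) are investigator judgements with no renal threshold.
- No other exclusion mentions GFR, clearance or renal disease.
- Inclusion 10 sets no upper age limit.

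No criterion therefore guarantees the property that Section 7.7.4 asserts.

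**Step 2. Can someone meet the first route with GFR below 30?**

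The documents give neither the institutional ULN nor a GFR equation. Assumptions: ULN 1.0, 1.1, 1.2 or 1.3 mg/dL, the same for both sexes, and CKD-EPI 2021, which is on the indexed scale that Section 7.7.4 uses:

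eGFR = 142 × min(Scr/κ, 1)^α × max(Scr/κ, 1)^−1.2 × 0.9938^age × 1.012 if female, with κ = 0.7 (women) or 0.9 (men) and α = −0.241 or −0.302.

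The ceiling of inclusion 15 is 1.5×ULN. Worked case, woman aged 70, ULN 1.2: Scr = 1.80, Scr/κ = 2.571, 2.571^−1.2 = 0.3220, 0.9938^70 = 0.6470. So eGFR = 142 × 0.3220 × 0.6470 × 1.012 = 29.9.

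eGFR at the ceiling (mL/min/1.73m²):

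| ULN (mg/dL) | Ceiling (mg/dL) | Woman 60 | Woman 70 | Woman 80 | Man 85 |
|---|---|---|---|---|---|
| 1.0 | 1.50 | 39.6 | 37.3 | 35.0 | 45.3 |
| 1.1 | 1.65 | 35.4 | 33.2 | 31.2 | 40.4 |
| 1.2 | 1.80 | 31.9 | 29.9 | 28.1 | 36.4 |
| 1.3 | 1.95 | 28.9 | 27.2 | 25.6 | 33.1 |

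At ULN 1.1 a woman of 85 is still at 30.3.

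**Step 3. How wide is the gap?**

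Solving for the creatinine at which a woman's eGFR equals 30, then dividing by 1.5 for the ULN at which the gap opens, and subtracting from the ceiling for its width (a negative width means no gap):

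| Age | Creatinine at eGFR 30 (mg/dL) | ULN needed (mg/dL) | Width at ULN 1.2 (mg/dL) | Width at ULN 1.3 (mg/dL) |
|---|---|---|---|---|
| 60 | 1.892 | 1.262 | −0.092 | 0.058 |
| 70 | 1.797 | 1.198 | 0.003 | 0.153 |
| 80 | 1.706 | 1.137 | 0.094 | 0.244 |

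The youngest woman below 30 at the ceiling is about 70 (69.7) at ULN 1.2 and about 54 (54.2) at ULN 1.3.

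**Step 4. Do the other safeguards close the gap?**

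The label commitment and the creatinine checks help. The hold, however, is triggered by a GFR that falls below 30 or a creatinine that rises above baseline. A subject who enters with a stable GFR below 30 shows neither, so coverage is unclear. The screening contrast scan may also be done 8 to 14 days before therapy, ahead of a creatinine due in the last 7 days.

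**The case against.** The case for leaving this alone has several parts.

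- **Few subjects, if any.** An affected subject must be an older woman just under the creatinine ceiling, at a site whose ULN is about 1.2 or higher, in a trial planned for 32. This stands, and it limits the weight of the point.
- **Outside inputs.** The sizes depend on an assumed ULN and equation. A lower, sex-specific ULN for women could remove the gap on this equation. This also stands for the sizes. The textual mismatch needs neither assumption.
- **The protocol already calls these patients ineligible.** An investigator reading Section 7.7.4 would not knowingly enrol one. But eligibility is judged against Section 4, which does not require GFR to be calculated, so a low GFR need not be known.
- **The hold plainly means no contrast below 30, whatever the course.** That is a sensible reading of its purpose, and Table 8 schedules chemistry at screening and on days 1 and 15 of Cycles 1 and 2, before the first restaging MRI. The trigger wording still does not say so for a subject who starts below 30.
- **An eligibility sentence cannot protect a scan done before eligibility is settled.** Correct. The screening scan needs a separate timing step, and contrast imaging may already have been done in routine care.
- **Section 7.7.4 could be corrected instead.** That would remove the contradiction, but it would give up the protection that the section claims.

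**Conclusion.** The concern holds. Section 7.7.4 attributes to Section 4 an exclusion that Section 4 does not make, and this follows from the text alone. The practical gap is small. With CKD-EPI 2021 it is absent at ULN 1.0 to 1.1 for women up to 85 and at every ULN tried for men up to 85. It is practically nil at age 70 with ULN 1.2, and reaches 0.24 mg/dL of creatinine at age 80 with ULN 1.3. Existing safeguards mitigate it in part. It is a minor safety and eligibility inconsistency that should be corrected because correction is cheap.

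**What to change.** Add one sentence to inclusion 15: every subject must have an estimated GFR of at least 30 mL/min/1.73m², calculated from the screening creatinine with a named equation. Leave the existing creatinine and clearance rule as it is.

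Preferably, have the result before any study-specific contrast scan, including the screening MRI. The eligibility sentence does not depend on this second step.

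Cost: screening creatinine and date of birth are already collected, so the calculation adds no test. If a study-specific MRI is done more than 7 days before therapy, the optional step needs an earlier creatinine or a recent clinical value. The downside is a rare screen failure, in a patient whom Section 7.7.4 already calls ineligible.
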